4.0 Background*

4.1 Provide the scientific or scholarly background, rationale, and significance of the research based on the existing literature and how it will contribute to existing knowledge. Describe any gaps in current knowledge. Include relevant preliminary findings or prior research by the investigator.

Response: Overproduction of cytokines and chemokines is believed to contribute to the development in COVID-19 disease (Zhang et al. 2020; Law et al. 2005; Cheung et al. 2005). Studies have shown in the blood of patients with COVID-19 there was a marked increase in the cytokines and chemokines interleukin 1 β (IL-1 β), interferon- γ (IFN- γ), interferon-inducible protein 10 (IP-10), monocyte chemoattractant protein 1 (MCP-1) and interleukin-4 (IL-4) (Huang et al. 2020; Zhang et al. 2020). Currently, the overall cumulative hospitalization rate is 20.0

per 100,000, with the highest rates in persons 65 years and older (63.8 per 100,000) and 50-64 years (32.8 per 100,000) (CDC 2020). Therefore, the majority of COVID-19 positive patients are not hospitalized and may have a milder course of disease. Consequently, methods that reduce the increase in cytokines that may result in severe course of disease, is necessary.

Melatonin, a pineal hormone, has been shown to have anti-inflammation, anti-oxidation and immune enhancing features (Andersen, et al. 2016). In multiple animal models of sepsis, acute lung injury, allergic asthma, respiratory syncytial virus (RSV) induced oxidative pulmonary injury, and ventilator-induced lung injury, melatonin supplementation has been shown to decrease the number of inflammatory cells, reduce the levels of the cytokines IL-4, IL-5, IL-13 and TNF- α and reduce nitric oxide and hydroxyl radical concentrations (Peng et al. 2018; Shin et al. 2014; Pedreira et al. 2008; Kim et al. 2012; Wu et al. 2012; Wang et al. 2018; Zhao et al. 2018; Aliasgharzadeh et al. 2019; Wu et al. 2020; Shang et al. 2009; Chen et al. 2011). In a randomized controlled trial, 8-week oral intake of 6 mg/d melatonin caused a significant decrease in serum levels of IL-6, TNF- α and C-reactive protein in subjects with diabetes mellitus and periodontitis (Bazyar et al. 2019). A significant decrease in TNF- α , IL-1b, IL-6, lipoperoxides and levels of nitric oxide catabolites occurred following oral administration of 25 mg/day melatonin for 6 months in subjects patients suffering from relapsing-remitting multiple sclerosis (Sanchez-Lopez et al. 2018). A meta-analysis of 22 randomized controlled trials indicates that melatonin supplementation significantly reduces the levels of TNF- α and IL-6 (Bazyar et al. 2019). Melatonin increases the proliferation and maturation of natural killer cells and other immune cells (Miller et al. 2006). This evidence supports the use of melatonin as a supplement to reduce the levels of cytokines in COVID-19 patients (Zhang et al., 2020).

4.2 Include complete citations or references.

Response:

Aliasgharzadeh, A., B. Farhood, P. Amini, H. Saffar, E. Motavaseli, S. Rezapoor, F. Nouruzi, D. H. Shabeeb, A. Elejo Musa, M. Mohseni, H. Moradi, and M. Najafi. 2019. 'Melatonin Attenuates Upregulation of Duox1 and Duox2 and Protects against Lung Injury following Chest Irradiation in Rats', *Cell J*, 21: 236-42.

Andersen, L. P., I. Gogenur, J. Rosenberg and R. J. Reiter (2016). "The Safety of Melatonin in Humans." *Clin Drug Investig* 36(3): 169-175.

5.0 Study Design*

5.1 *Describe and explain the study design (e.g. case-control, cross-sectional, ethnographic, experimental, interventional, longitudinal, observational).*

Response: placebo-controlled randomized double-blind pilot trial

6.0 Study Intervention/Investigational Agent

1.1 Description: *Describe the study intervention and/or investigational agent (e.g., drug, device) that is being evaluated.*

Response: Melatonin (5-methoxy-N-acetyl tryptamine)

6.1 *Drug/Device Handling: If the research involves drugs or device, describe your plans to store, handle, and administer those drugs or devices so that they will be used only on subjects and be used only by authorized investigators.*

- *If the control of the drugs or devices used in this protocol will be accomplished by following an established, approved organizational SOP (e.g., Research Pharmacy SOP for the Control of Investigational Drugs, etc.), please reference that SOP in this section.*

Response:

Melatonin is a synthetic product with white physical appearance. Melatonin is sold as a food supplement for use in humans. This study will use Melatonin Tablets (10 mg per capsules) purchased from Life Extension (Northeast Fulfillment, Inc, Edison, NJ 08837) (see certificate of analysis attached) and shipped directly to research pharmacist and stored in the research pharmacy in the CRC.

Melatonin will be administered as a 10 mg dose three times a day for 14 days. Capsules (size “4” Clear Vegetable cellulose capsule with off-white fill) containing 10 mg melatonin, microcrystalline cellulose, and rice concentrate prepared by Life Extension® (Northeast Fulfillment, Inc, Edison, NJ 08837) will be over-encapsulated in opaque gelatin capsules. Placebo capsules will be prepared with identical opaque gelatin capsules using methylcellulose. Both melatonin and placebo capsules will be given orally. Over-encapsulation of placebo and melatonin treatments will be done by the research pharmacist and will be mailed to study subjects directly by courier.

Melatonin capsules will be stored at room temperature.

Placebo capsules will be stored at room temperature.

6.2 *If the drug is investigational (has an IND) or the device has an IDE or a claim of abbreviated IDE (non-significant risk device), include the following information:*

- *Identify the holder of the IND/IDE/Abbreviated IDE.*
- *Explain procedures followed to comply with sponsor requirements for FDA regulated research for the following:*

FDA Regulation	Applicable to:		
	IND Studies	IDE studies	Abbreviated IDE studies
21 CFR 11	X	X	
21 CFR 54	X	X	
21 CFR 210	X		
21 CFR 211	X		
21 CFR 312	X		
21 CFR 812		X	X
21 CFR 820		X	

Response: IND approved

7.0 Local Number of Subjects

7.1 *Indicate the total number of subjects that will be enrolled or records that will be reviewed locally.*

Response: 30

7.2 *If applicable, indicate how many subjects you expect to screen to reach your target sample (i.e. your screen failure rate).*

Response: 60

7.3 *Justify the feasibility of recruiting the proposed number of eligible subjects within the anticipated recruitment period. For example, how many potential subjects do you have access to? What percentage of those potential subjects do you need to recruit?*

Response: There are approximately 50 to 100 + COVID results reported daily in Erie County. In addition, many more individuals with COVID symptoms do not get tested. In order to facilitate enrollment and determination of subject eligibility, those with symptoms of COVID-19 within 5 days that have not received a test or its result will be given a rapid antigen test to confirm eligibility for the study.

8.0 Inclusion and Exclusion Criteria*

8.1 *Describe the criteria that define who will be **included** in your final study sample.*

NOTE: This may be done in bullet point fashion.

Response:

- a. Male or non-pregnant female adult ≥ 18 years of age at time of enrolment.
- b. Women of childbearing potential must agree to use at least one primary form of contraception for the duration of the study.
- c. Onset of COVID-19 Symptoms within 5 days
- d. Positive testing for COVID-19 infection by standard RT-PCR assay or equivalent test within 5 days or willingness to receive a rapid antigen test (EUA Nasal swab antigen test) by the study team. Following enrollment, among subjects that have not received a COVID test yet or its results, a nasopharyngeal swab sample will be obtained and a rapid antigen test (**CareStart™ COVID-19 Antigen Test**) by the study team.
- e. Meets criteria for mild or moderate COVID disease defined as follows:
Mild COVID-19
 - Symptoms of mild illness with COVID-19 that could include fever, cough, sore throat, malaise, headache, muscle pain, gastrointestinal symptoms, without shortness of breath or dyspnea
 - No clinical signs indicative of Moderate, Severe, or Critical Severity**Moderate COVID-19**
 - Symptoms of moderate illness with COVID-19, which could include any symptom of mild illness or shortness of breath with exertion
 - Clinical signs suggestive of moderate illness with COVID-19, such as respiratory rate ≥ 20 breaths per minute, saturation of oxygen (SpO_2) $> 93\%$ on room air at sea level, heart rate ≥ 90 beats per minute.
 - No clinical signs indicative of Severe or Critical Illness Severity
- f. Subject provides written informed consent prior to initiation of any study procedures.
- g. Understands and agrees to comply with planned study procedures.
- h. Agrees to the collection and storage of saliva samples per protocol.
- i. Subject agrees to provide an emergency contact who the study team can contact in case the subject is not reachable on any of the study visits

8.2 *Describe the criteria that define who will be **excluded** from your final study sample.*

NOTE: This may be done in bullet point fashion.

Response:

- a. Severe chronic kidney disease ($eGFR < 30$ ml/min) or Moderate renal impairment ($eGFR 30-60$ ml/min) or requiring dialysis
- b. Severe hepatic insufficiency defined as one or more of the following: Cirrhosis diagnosis, Serum ALT $> 3x$ ULN or Alkaline phosphatase $> 3x$ ULN or bilirubin $> 2x$ ULN in the absence of Gilbert's or hemolysis, Uncontrolled acute or chronic liver disease (e.g. acute hepatitis A, unstable autoimmune hepatitis)
- c. Pregnancy or breast feeding.
- d. History of a seizure disorder.
- e. Patient is taking Fluvoxamine, Capmatinib, Ciprofloxacin (Systemic),

Deferasirox, Givosiran, Methoxsalen (Systemic), Mexiletine, Rucaparib, Stiripentol, Thiabendazole, Vemurafenib, Methoxsalen, Sodium oxybate or Echinacea.

- f. Allergy to the study medication
- g. Currently taking melatonin
- h. Currently taking high dose (>500 mg/day) Vitamin C.
- i. Meets criteria for Severe or Critical COVID-19 infection defined as follows:

Severe COVID-19

- Symptoms suggestive of severe systemic illness with COVID-19, which could include any symptom of moderate illness or shortness of breath at rest, or respiratory distress
- Clinical signs indicative of severe systemic illness with COVID-19, such as respiratory rate ≥ 30 per minute, heart rate ≥ 125 per minute, $\text{SpO}_2 \leq 93\%$ on room air at sea level or $\text{PaO}_2/\text{FiO}_2 < 300$
- No criteria for Critical Severity

Critical Covid-19

- Evidence of critical illness, defined by at least one of the following:
 - Respiratory failure defined based on resource utilization requiring at least one of the following:
 - Endotracheal intubation and mechanical ventilation, oxygen delivered by high-flow nasal cannula (heated, humidified, oxygen delivered via reinforced nasal cannula at flow rates > 20 L/min with fraction of delivered oxygen ≥ 0.5), noninvasive positive pressure ventilation, ECMO, or clinical diagnosis of respiratory failure (i.e., clinical need for one of the preceding therapies, but preceding therapies not able to be administered in setting of resource limitation)
 - Shock (defined by systolic blood pressure < 90 mm Hg, or diastolic blood pressure < 60 mm Hg or requiring vasopressors)
 - Multi-organ dysfunction/failure

8.3 *Indicate specifically whether you will include any of the following special populations in your study using the checkboxes below.*

NOTE: Members of special populations may not be targeted for enrollment in your study unless you indicate this in your inclusion criteria.

Response:

- Adults unable to consent
- Individuals who are not yet adults (infants, children, teenagers)
- Pregnant women
- Prisoners

8.4 *Indicate whether you will include non-English speaking individuals in your study. Provide justification if you will exclude non-English speaking individuals.*

*In order to meet one of the primary ethical principles of equitable selection of subjects, non-English speaking individuals may **not** be routinely excluded from research as a matter of convenience.*

In cases where the research is of therapeutic intent or is designed to investigate areas that would necessarily require certain populations who may not speak English, the researcher is required to make efforts to recruit and include non-English speaking individuals. However, there are studies in which it would be reasonable to limit subjects to those who speak English. Some examples include pilot studies, small unfunded studies with validated instruments not available in other languages, studies with numerous questionnaires, and some non-therapeutic studies which offer no direct benefit.

Response: Because of the pilot nature of this proposal with limited funding, we are not including non-English speaking individuals. However, if this pilot project leads to a larger study, such subjects will be included.

9.0 Vulnerable Populations*

If the research involves special populations that are considered vulnerable, describe the safeguards included to protect their rights and welfare.

NOTE: You should refer to the appropriate checklists, referenced below, to ensure you have provided adequate detail regarding safeguards and protections. You do not, however, need to provide these checklists to the IRB.

9.1 *For research that involves **pregnant women**, safeguards include:*

NOTE CHECKLIST: Pregnant Women (HRP-412)

Response:

N/A: This research does not involve pregnant women.

9.2 *For research that involves **neonates of uncertain viability or non-viable neonates**, safeguards include:*

NOTE CHECKLISTS: Non-Viable Neonates (HRP-413), or Neonates of Uncertain Viability (HRP-414)

Response:

N/A: This research does not involve non-viable neonates or neonates of uncertain viability.

9.3 *For research that involves **prisoners**, safeguards include:*

NOTE CHECKLIST: Prisoners (HRP-415)

Response:

N/A: This research does not involve prisoners.

9.4 *For research that involves persons who have not attained the legal age for consent to treatments or procedures involved in the research (“children”), safeguards include:*

NOTE CHECKLIST: Children (HRP-416)

Response:

N/A: This research does not involve persons who have not attained the legal age for consent to treatments or procedures (“children”).

9.5 *For research that involves cognitively impaired adults, safeguards include:*

NOTE CHECKLIST: Cognitively Impaired Adults (HRP-417)

Response:

N/A: This research does not involve cognitively impaired adults.

9.6 *Consider if other specifically targeted populations such as students, employees of a specific firm, or educationally or economically disadvantaged persons are vulnerable. Provide information regarding their safeguards and protections, including safeguards to eliminate coercion or undue influence.*

Response: Not applicable as no population will be specifically targeted.

10.0 Eligibility Screening*

10.1 *Describe screening procedures for determining subjects’ eligibility. Screening refers to determining if prospective participants meet inclusion and exclusion criteria.*

 *Include all relevant screening documents with your submission (e.g. screening protocol, script, questionnaire).*

Response: Patients that have COVID-19 Symptoms within 5 days will be assessed for eligibility. All screening procedures will take place entirely remotely by phone. Screening will begin with a brief presentation about the study followed by a screening checklist. We will rely on patient’s statements over the phone to ensure they meet inclusion and exclusion criteria. Individuals who meet the inclusion and exclusion criteria and are interested in participating in the study will then proceed to providing informed consent at the in person visit. Once consented, a subject that has not had a COVID-19 test will be given a rapid antigen test. This test is done on a nasopharyngeal swab sample. Those that test positive will continue in the study; those who test negative will be removed from the study.

N/A: There is no screening as part of this protocol.

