1.0 Study Summary

Study Title	A pilot placebo-controlled randomized double-blind trial of Melatonin in outpatients with COVID infection.
Study Design	This study is a pilot randomized, double-blind, placebo-controlled clinical trial to evaluate the safety and efficacy of melatonin in outpatient adult patients suspected to be afflicted with COVID-19.
Primary Objective	Evaluate the safety of the intervention through 42 days of follow-up as compared to the control arm as assessed by: 
• Cumulative incidence of serious adverse events (SAEs)• Cumulative incidence of Grade 3 and 4 adverse events (AEs).• Adverse Events of Special Interest• Discontinuation or temporary suspension of the investigational medication (for any reason).
Secondary Objective(s)	Evaluate the clinical efficacy of melatonin as compared to placebo as assessed by: Hospitalization Incidence of COVID related hospitalization at 42 days. Data will be obtained from electronic medical record. COVID related symptoms The speed of resolution of COVID related symptoms Change from baseline Day 1 to Day 42. Change in the WHO Clinical Progression Scale (0-10). Data will be obtained from electronic medical record. Mortality 42-day mortality. Data will be obtained from electronic medical record.

Research Intervention(s)/Investigational Agent(s)	Melatonin (5-methoxy-N-acetyl tryptamine)
IND/IDE #	150700
Study Population	Outpatient adult (≥ 18 years old) patients with COVID-19.
Sample Size	30 subjects
Study Duration for individual participants	42 days
Study Specific Abbreviations/Definitions	COVID-19: Coronavirus Disease 2019

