3.0 Scientific Endpoints*

2.1 Describe the scientific endpoint(s), the main result or occurrence under study.

*NOTE: Scientific endpoints are outcomes defined before the study begins to determine whether the objectives of the study have been met and to draw conclusions from the data. Include primary and secondary endpoints. Some example endpoints are: reduction of symptoms, improvement in quality of life, or survival. Your response should **not** be a date.*

Response:

Primary Objective

Evaluate the safety of the intervention through 42 days of follow-up as compared to the control arm as assessed by:

- Cumulative incidence of serious adverse events (SAEs)
- Cumulative incidence of Grade 3 and 4 adverse events (AEs).

- Adverse Events of Special Interest
- Discontinuation or temporary suspension of the investigational medication (for any reason).

Secondary Objectives

Evaluate the clinical efficacy of melatonin as compared to placebo as assessed by:

Hospitalization: Incidence of COVID related hospitalization at 42 days.

Data will be obtained from electronic medical record.

COVID related symptoms: Fever, chills, cough, nasal symptoms, body aches/muscle aches, headache, loss of smell, loss of taste, nausea, vomiting, diarrhea, fatigue, dizziness. The speed of resolution of COVID related symptoms. Change from baseline, Day 1 to Day 42. Accessed by questionnarre.

Change in the WHO Clinical Progression Scale (0-10). Data will be obtained from electronic medical record.

Mortality: 42-day mortality. Data will be obtained from electronic medical record.

Exploratory Objective

Evaluate the effect of melatonin on virologic parameters as compared to placebo and assessed by:

-Percent of subjects with SARS-CoV-2 detectable in saliva sample at days 1, 3, 7, 14, 28 and 42.

-Quantitative RT-PCR for SARS-CoV-2 virus in saliva sample at days 1, 3, 7, 14, 28 and 42.

-Evaluate the reduction in cytokine/chemokine RNA and/or protein levels in saliva:

-Reduction as compared to baseline (Day 1) in salivary levels of cytokine/chemokine RNA and/or protein (IL-1, IL-2, IL-3, IL-4, IL-6, IL-8, IL-10, IL-11, IL-12, IL-13, IL-17, IL-18, TNF α , IFNy, IFN α , IFN-B, MCP1) at days 3, 7, 14, and 28.

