12.0 Procedures Involved*

12.1 Provide a description of *all research procedures or activities* being performed and when they are performed once a subject is screened and determined to be eligible. Provide as much detail as possible.

NOTE: This should serve as a blueprint for your study and include enough detail so that another investigator could pick up your protocol and replicate the research. For studies that have multiple or complex visits or procedures, consider the addition of a schedule of events table in in your response.

Response: Because of the highly contagious nature of COVID infection in the first few days after onset of symptoms, it is essential to minimize exposure of research team members to the subjects. Therefore, except for the enrollment visit, all procedures for this study will be conducted remotely at the subject's home. The Table below depicts all the research procedures.

	Screen	Enrollment							
Day +/- Window	-1 or 1	1	Daily until	Daily until	Day 3 ± 1	Day 7 ± 1	Day 14 ± 2	Day 28 ± 3	Day 42 ± 3

			day 14	day 42					
Assessments/Procedures									
ELIGIBILITY									
Informed consent	X								
Demographics & Medical History	X								
Prior SARS-CoV-2 based on screening or perform rapid antigen testing	X								
STUDY INTERVENTION									
Randomization		X							
Administration of Melatonin/Placebo		X	X						
STUDY PROCEDURES									
Body temperature		X	X	X	X	X	X	X	X
Clinical data collection		X	X	X	X	X	X	X	X
Pulse Oximetry measurement		X	X	X	X	X	X	X	X
Adverse event evaluation		X			X	X	X	X	X
RESEARCH LABORATORY									
Saliva for PCR SARS-CoV-2		X			X	X	X	X	X
Saliva for Cytokine/Chemokine RNA and/or protein		X			X	X	X	X	X

Below is a day by day description of the study procedures.

- For those subjects that have not had a COVID-test: Subjects will be enrolled and then tested for SARS-CoV2 using an EUA rapid antigen administered by the study team. If negative by rapid antigen test subjects will be withdrawn from study. Those subjects that have a prior positive test will not be give a rapid antigen test.
- If COVID-19 positive:
- Collect a baseline sample of saliva prior to taking drug, by spitting in a collection container that will be provided at time of consent.
- Rate COVID symptoms before starting medication and then each day in the evening on a short questionnaire from Day 1 to Day 42.
- Record body temperature and pulse oximetry each day in the morning and evening.

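### Eligibility rests on phone statements without a planned record or oximeter check before randomisation, and no rule says that an admission or death reported on a call counts if the EMR does not show it

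*Combined protocol and SAP*

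**What the plan says.** **Eligibility.** Section 10.1 makes screening a telephone procedure and relies on the patient's "statements over the phone to ensure they meet inclusion and exclusion criteria"; consent follows at an in-person visit. The criteria in 8.1 and 8.2 include limits on eGFR, ALT, alkaline phosphatase, bilirubin, SpO2, respiratory rate and heart rate. Section 12.4 plans EMR access for baseline health information. The 12.1 schedule marks oximetry in the Day 1 enrolment column, the same column as randomisation, and 14.1 has the oximeter handed over at consent.

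**COVID-19 status.** Four places describe who gets the rapid antigen test:

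- 7.3: those "that have not received a test or its result will be given a rapid antigen test".
- 8.1, criterion d: "among subjects that have not received a COVID test yet or its results".
- 10.1: "a subject that has not had a COVID-19 test will be given a rapid antigen test".
- 12.1: "Those subjects that have a prior positive test will not be give a rapid antigen test".

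**Outcomes.** Section 1.0 gives "Incidence of COVID related hospitalization at 42 days. Data will be obtained from electronic medical record". Section 3.0 gives "Change in the WHO Clinical Progression Scale (0-10). Data will be obtained from electronic medical record" and "Mortality: 42-day mortality. Data will be obtained from electronic medical record". Section 19.1 also analyses hospitalisation for any reason and names no source for it. Calls are scheduled on Days 3, 7, 14, 28 and 42 (12.1), and 21.4 collects safety information by phone. Section 21.2 has a blinded external reviewer judge whether observed hospitalisations were COVID related. Section 21.9 makes a hospitalisation rate well above 20% a condition for suspending the study.

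**The concern.** A caller may not know a recent eGFR or bilirubin, or be able to state an oxygen saturation. If the text is followed as written, a subject who meets an exclusion, or whose positive test was misremembered or older than 5 days, can be randomised.

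On outcomes, subjects are followed at home and recruited partly through social media, a volunteer registry and community events (11.1), so they need not belong to one health system. An admission or death outside the accessible records leaves no EMR entry and can look like a non-event. The missing-data paragraph in 19.1 would not necessarily catch this, because nothing appears to be missing. WHO scores for subjects who stay at home may also be hard to obtain from an EMR. Section 19.1 says the estimates are meant for planning later trials, so rates that read too low would carry forward.

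**Working it through.** **Inputs.** From the documents: 30 subjects (1.0, 7.1), randomised 2:1 (19.1), hence 20 and 10; anticipated hospitalisation 20% (21.1); Clopper-Pearson 95% intervals (19.1). The documents give no rate of misreporting, EMR capture or detection by call. Those three are assumptions, shown as ranges.

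**The plan's own figure.** Section 19.2 puts the largest standard error with 20 subjects at 11 percentage points. sqrt(0.5 × 0.5 / 20) = 0.1118, or 11.2 points, which agrees after rounding. Nothing below changes it.

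**Expected admissions at 20%.** 20 × 0.20 = 4 and 10 × 0.20 = 2, so 6 in all.

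**EMR capture c (assumed).** The rate read from the EMR alone is 0.20c. The chance that at least one admission is absent from the EMR is 1 − (1 − 0.20(1 − c))^30. If an event from either source counts, and calls independently detect a share d = 0.80 (assumed), the chance of missing at least one is 1 − (1 − 0.20(1 − c)(1 − d))^30.

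| c | Rate read from EMR | At least one absent from EMR | At least one missed, either source counts |
|---|---|---|---|
| 0.95 | 19% | 26% | 6% |
| 0.90 | 18% | 45% | 11% |
| 0.80 | 16% | 71% | 21% |
| 0.70 | 14% | 84% | 30% |

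The third column is an upper bound on missed admissions, because calls may bring some to light under the current plan too.

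**One missed event.**

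- Melatonin arm: 4/20 = 20% (CI 5.7% to 43.7%) becomes 3/20 = 15% (3.2% to 37.9%).
- Placebo arm: 2/10 = 20% (2.5% to 55.6%) becomes 1/10 = 10% (0.3% to 44.5%).

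Both shifts lie well inside the intervals.

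**Eligibility misstatement r (assumed).** The expected number ineligible is 30r, and the chance of at least one is 1 − (1 − r)^30. For r = 1%, 2%, 5% and 10% this gives 0.3, 0.6, 1.5 and 3.0 subjects, and 26%, 45%, 79% and 96%. The range is wide because the documents do not narrow it.

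**Testing passages side by side.** A subject who has been tested and awaits the result is tested under 7.3 and 8.1. Under 10.1 and 12.1 that subject has already had a test, so is not in the group to be tested, and has no prior positive either, so is not in the exempt group.

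**The case against.** The strongest reply is that much of this is already handled. The endpoint lines do not exclude other sources. Section 12.1 schedules clinical data collection on the call days, 12.3 lists a follow-up form and the WHO scale, and 21.4 gathers safety data by phone, so an admission would probably come to light. The screening checklist and the data forms are not in the documents and may ask for these items. That stands, and it limits the outcome part to a missing rule for a call report that the EMR does not confirm.

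Several stronger readings are tempting but not supported:

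- *The EMR will miss events.* Section 12.4 speaks only of the relevant EMRs; coverage is unstated, not shown to be poor.
- *A pre-randomisation oximeter check is already planned.* The device is handed over at consent and subjects log readings at home, so the Day 1 value could be a home entry. No passage puts it before randomisation.
- *A reported positive test is left unaddressed.* Read together, 10.1 and 12.1 accept it. The weakness is that it is not confirmed.
- *The adjudicator and emergency contact are planned outcome sources.* The adjudicator classifies admissions already observed. The emergency contact (8.1, criterion i) is for unreachable subjects and has no assigned outcome role.

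It is also fair to say that remote conduct has a stated reason, limiting staff exposure to contagious subjects (12.1, 14.1).

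**Conclusion.** The point holds as a worthwhile, inexpensive improvement. Section 10.1 lets unverified statements settle laboratory and vital-sign criteria without using record access that is already planned, and the testing passages disagree on pending results. Sections 1.0 and 3.0 name the EMR for three endpoints with no rule for events learned on a call, and any-reason hospitalisation has no named source.

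The likely direction is event rates that are somewhat too low: 19% to 14% instead of 20% at an assumed 95% to 70% capture if the EMR alone is used. The true size cannot be derived from the documents. A reader might infer bias in favour of one arm, but the procedures are the same in both blinded arms and none is expected. The EMR endpoints are secondary. The primary safety outcomes are collected by phone and do not depend on the EMR source, and the precision statement in 19.2 is unaffected.

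**What to change.** **In 10.1**, before randomisation, check the existing criteria wherever a source exists: the EMR or a shown report for the prior positive test and its date, the EMR for the renal and liver criteria, and an oximeter reading taken at the in-person visit for SpO2 and pulse. Report, for each criterion, how many subjects met it by self-report only.

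**Reconcile** 7.3, 8.1, 10.1 and 12.1 on subjects whose test result is pending.

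**In 1.0 and 3.0**, ascertain hospitalisation (COVID related and for any reason), vital status and the WHO scale from the Day 3, 7, 14, 28 and 42 calls as well as the EMR, using the emergency contact if the subject cannot be reached. Count an event found by any source, send every admission to the existing blinded adjudicator to classify COVID-relatedness, and report how many events lack EMR confirmation. State in 21.9 that the same count is used there.

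**Cost.** No new tests or visits, but several added call items and record checks, and a few more minutes at the one face-to-face visit, which has to be weighed against the plan's wish to limit staff exposure. There may be a few more screen failures, and some events will be counted on report alone. Laboratory criteria and respiratory rate will remain unverified where no record exists.
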